1. INTRODUCTION

1.1. Background Information and Study Rationale

1.1.1. Background Information

Psoriasis is a common, chronic relapsing inflammatory skin disease [Parisi, 2012] with recurrent episodes of prominently erythematous and scaly patches (plaques). Approximately 2% to 3% of the global population is affected by psoriasis; those affected are predominantly adults, who are most often diagnosed between the ages of 18 to 35 years. Psoriasis disrupts daily activities such as work and/or school attendance, interpersonal relationships, recreational activities, and intimacy – thereby significantly impacting sufferers' quality of life. Furthermore, psoriasis sufferers can also have co-morbidities such as arthritis, depression, inflammatory bowel disease, and cardiovascular diseases.

Up to 80% of patients have mild to moderate plaque-type psoriasis, which is generally managed with topical treatments. The most commonly used treatments for psoriasis include topically applied corticosteroids and Vitamin D analogs, alone or in combination. Vitamin D analogs are moderately efficacious as monotherapy, while application of topical corticosteroids – particularly the very potent ones – is restricted in terms of body areas that can be treated and the duration of use due to the well-known application site and systemic adverse drug reactions [Mason, 2013]. Although numerous topical treatment options are available, there remains a need for a topical treatment that combines a high level of efficacy with an acceptable safety profile that permits application to a large body surface area (BSA) without restrictions on duration of treatment.

DMVT-505 (tapinarof), formerly known as GSK2894512, is a fully synthetic hydroxylated stilbene that is being developed by Dermavant Sciences GmbH (Dermavant) as a novel anti-inflammatory agent for the topical treatment of atopic dermatitis (AD) and plaque psoriasis. The compound (number WBI-1001) was initially developed by Welichem Biotech Inc. (Welichem; Burnaby, British Columbia, Canada) and then was acquired by GlaxoSmithKline (GSK) on 31 July 2012 for further development in the rest of the world except China. Beijing Wenfeng Tianji Pharmaceuticals (BWTP) is developing a compound in China identified as Benvitimod (active ingredient corresponds to tapinarof) with a unique topical formulation. Dermavant acquired the drug from GSK on 20 August 2018 for continued development.

Tapinarof cream, 1% is a white to off-white, oil-in-water emulsion intended for topical application to AD and psoriatic skin lesions, which has a novel mechanism of action. The drug likely mediates its effects via the aryl hydrocarbon receptor (AhR) agonist and nuclear factor-erythroid 2-related factor-2 (Nrf2) because the pattern of pro-inflammatory mediators inhibited by tapinarof is different from that of corticosteroids, calcineurin inhibitors, vitamin D analogs, and other immunosuppressive agents commonly used to treat AD and psoriasis. Rather, the profile of biological responses elicited by tapinarof most closely matches that of the dual activation properties of coal tar, a common nonprescription treatment for psoriasis. Together, existing data identify tapinarof as a non-steroid, therapeutic AhR-modulating agent (TAMA), which is a unique mechanism of action compared with existing therapies.

Tapinarof cream has been evaluated in nonclinical studies at concentrations up to 8% and in clinical studies at concentrations up to 2%. Three Phase I clinical pharmacology studies in healthy volunteers and 7 Phase I/II studies in subjects with AD and psoriasis have been completed. Refer to the current version of the tapinarof Investigator's Brochure for detailed information. Tapinarof has demonstrated an acceptable safety profile and a clear therapeutic effect, as compared to vehicle, in both psoriasis and AD.

Four randomized, double-blind, vehicle-controlled, clinical studies to evaluate the safety and efficacy of topically-applied tapinarof cream in subjects with AD or psoriasis were conducted by Welichem; one 28-day and one 12-week study was completed for each indication.

These studies enrolled a total of 282 adult subjects, with 235 subjects exposed to tapinarof cream 0.5%, 1%, or 2% (Formulation C) once or twice daily for a period of 28 to 84 days. Efficacy was rapid, and statistically significant differences versus vehicle were observed as early as Day 14 for the majority of efficacy parameters in both indications. The most frequently reported (1 to 6% of 235 subjects) dermatological adverse events (AEs), regardless of causality, were application site discoloration/hyperpigmentation, application site dermatitis, papular rash, pruritus, dermatitis contact, folliculitis, erythema, and skin burning sensation. Nasopharyngitis and headache were the most frequently-reported (>10% of subjects) nondermatological AEs overall. Overall, results of the clinical studies indicated tapinarof was highly efficacious for both AD and psoriasis, with a favorable safety profile.

The first clinical study with Formulation F (Study 201851) was a Phase 1 study to evaluate the systemic exposure and pharmacokinetic (PK) parameters of tapinarof cream, 1% and 2%. This study was conducted in 11 subjects with AD; 5 subjects were treated with the 2% dose and 6 subjects were treated with the 1% dose. Headache was the most frequently reported (100% and 60% of subjects at the 1% and 2% doses, respectively) nondermatological adverse event.

Two Phase 2b, 12-week, randomized, double-blind, vehicle-controlled, 6-arm, parallel-group, dose-finding studies with topically applied tapinarof cream were conducted by GSK; 1 study each in subjects with AD or psoriasis. These 2 studies evaluated the safety and efficacy of tapinarof cream (Formulation F) at 2 concentrations (0.5% or 1%) and 2 application frequencies (once daily or twice daily) in 247 adult and adolescent subjects with AD and in 227 adult subjects with plaque psoriasis.

In both studies, tapinarof showed a clear therapeutic effect compared with vehicle, with the 1% concentration treatment groups demonstrating a higher proportion of subjects with treatment success compared with the 0.5% concentration groups (applied once daily and twice daily in the AD study). In both indications, the tapinarof 1% dosing groups showed a faster onset of action than the 0.5% dosing groups, and once daily application had similar efficacy to twice daily application. In both Phase 2b studies, tapinarof showed an acceptable safety profile. Treatment-emergent adverse events (TEAEs) were reported with a higher frequency in the tapinarof groups than in the vehicle groups. The most frequent TEAEs ($\geq 5\%$ in any arm or in total) were nasopharyngitis, folliculitis, dermatitis contact, atopic dermatitis, upper respiratory tract infection, headache, vomiting, acne, application site dermatitis, miliaria, dermatitis allergic, and impetigo. The majority of TEAEs were mild or moderate in severity. In each study, the tapinarof 1% once daily treatment group had a lower frequency of TEAEs than the tapinarof 1% twice daily treatment group.

1.1.2. Study Rationale

This 40-week, Phase 3, open-label extension study is being conducted as part of a clinical development program to evaluate the long-term safety and continued efficacy of tapinarof cream, 1% for the topical treatment of plaque psoriasis in adults with psoriasis. Subjects in this study will be selected from those subjects who complete 1 of 2 Phase 3 pivotal efficacy and safety studies (pivotal Study DMVT-505-3001 or pivotal Study DMVT-505-3002) and meet the predefined criteria to enroll into this study.

1.2. Rationale for Study Design and Dose

As in the pivotal studies, this Phase 3 study continued to be conducted at multiple study centers in more than 1 country to enhance the possibility of inclusion of a wider range of population groups and to subsequently increase generalizability of the results. Tapinarof cream is intended for long-term, intermittent use in non-life-threatening inflammatory dermatologic conditions. Therefore, the 40-week duration of long-term, intermittent use of tapinarof in this study, in addition to the treatment received in the pivotal study, is expected to be an adequate duration to assess safety and efficacy of repeated treatment courses of tapinarof as recommended in the International Conference on Harmonisation E1 (ICH E1) guideline on the extent of population exposure to assess clinical safety for drugs intended for long-term treatment of non-life-threatening conditions [ICH, 1994], which recommends a minimum of 100 subjects be treated with the intended clinical dose and to be followed for AEs over at least 1 year.

The once daily topical application of tapinarof cream, 1% concentration administered in the pivotal studies will be continued in this open-label extension study.

1.3. Potential Risks and Benefits

To assess any potential impact on subject eligibility with regard to safety, the Investigator must refer to the current version of the tapinarof Investigator's Brochure for detailed information regarding warnings, precautions, contraindications, AEs, and other significant data pertaining to the study drug being used in this study.

1.3.1. Risk Assessment

1.3.1.1. Dermatological Adverse Events, Including Skin Irritation or Allergic Reaction

Tapinarof or its excipients may induce skin irritation. Allergic or irritant reactions in the exposed areas may present as erythema, edema, papules, or vesicles. In the event of pronounced skin reaction, spreading of the eczematous reaction beyond the original application site(s) and/or more generalized (remote) skin reactions may be observed.

In the dose-ranging study 203120 in psoriasis, the most frequently reported dermatologic AEs were folliculitis and contact dermatitis. In the dose-ranging study 203121 in AD, the most frequently reported dermatologic AEs were folliculitis and AD. Nonclinical dermal toxicity studies of up to 8% tapinarof for up to 13 weeks indicated local effects are primarily mild to moderate skin irritation that is reversible; tapinarof did not show evidence of sensitization. In initial clinical studies using a different formulation of tapinarof (Formulation C), AEs of skin

hyperpigmentation, application site dermatitis, papular rash, pruritus, contact dermatitis, folliculitis, erythema, and skin burning sensation were reported.

To mitigate these potential risks, subjects with a known or suspected intolerance to tapinarof or its excipients will be excluded from enrollment. Subjects' skin will be evaluated routinely for signs of irritation or allergic reaction, and if needed, study treatment will be interrupted and an appropriate treatment provided. Note that after cessation of exposure, dermatological reactions generally subside spontaneously or with topical treatments.

1.3.1.2. Systemic Adverse Events

Nasopharyngitis and headache were the most frequently reported nondermatological AEs in dose-ranging Study 203120 in psoriasis. In dose-ranging Study 203121 in AD, the most frequently reported nondermatological AEs were nasopharyngitis, upper respiratory tract infection, and headache. In the initial clinical studies (in AD and psoriasis) using a different tapinarof formulation (Formulation C), nasopharyngitis and headache were the most frequently reported nondermatological AEs. In the open-label PK Study 201851 with BID dosing of Formulation F of tapinarof cream (n=11), 1% and 2%, headache was the most frequently reported AE during the study (reported for 100% and 60% of subjects at the 1% and 2% doses, respectively).

In a nonclinical study in minipigs using intravenous (IV) administration, reversible decreases in arterial blood pressure and PR interval were observed; however, in this study and repeat dermal toxicity studies, there were no effects on QT interval or heart rate. Repeat-dose dermal toxicity studies also showed findings related to the liver (increased weights and hepatocellular hypertrophy/regeneration) and thymus (thymic cortex depletion in adult rabbits and rats; changes in thymus weight, microscopic decreased cellularity, and changes in thymic T cell maturation in juvenile rats) with associated secondary hematological findings. Thymic findings were also noted in repeat adult and juvenile rat studies; however, there were no clinically relevant AEs/SAEs reported.

To mitigate potential systemic risks, subjects will be monitored for AEs and any abnormal vital signs, physical examination, and laboratory test results.

1.3.1.3. Reproductive and Developmental Toxicity

Results of embryo-fetal development studies in rats and rabbits indicated an increased risk for embryo-fetal developmental effects, as evidenced by an increase in post-implantation loss and incidence of fetal skeletal variations. Results of a juvenile rat study indicated adverse microscopic changes in the form of renal pelvic dilatation in both sexes, along with reversible increases in total urinary glucose and protein excretion in males at $\geq 10/15$ mg/kg/day tapinarof (administered subcutaneously).

An investigative study in rats suggested an increased risk for hydronephrosis during a narrow window of postnatal sensitivity prior to postnatal day (PND) 32 (specifically PND 15 to 21). Rat renal tubule anatomic maturation and nephrogenesis occurs during this period [Cappon, 2010; Frazier, 2013; Zoetis, 2003], however tubule morphogenesis/nephrogenesis occurs entirely prenatally in humans [Cappon, 2010; Zoetis, 2003].

To mitigate these potential risks, women of childbearing potential (CBP) must utilize abstinence or a highly effective method of contraception consistently and correctly during the study and for 4 weeks after the end of treatment (Section 4.2). Monthly pregnancy testing will be conducted. Pregnant women and subjects under 18 years of age will be excluded from the study. If a woman becomes pregnant during the study, she will immediately discontinue study treatment. Additionally, AEs will be monitored and clinical laboratory testing will be performed.

1.3.2. Benefit Assessment

Subjects may experience improvements in their psoriasis during the course of the study and may benefit from the additional safety assessments conducted as part of the study (e.g., physical examination, laboratory tests). Subjects in the study will also contribute to the process of developing a novel anti-inflammatory agent for the topical treatment of psoriasis.

1.3.3. Overall Benefit/Risk

Taking into account the measures taken to minimize risk to subjects in this study, the potential risks identified in association with tapinarof are justified by the anticipated benefits that may be afforded to subjects with psoriasis.

2. OBJECTIVES AND ENDPOINTS

The objectives and associated endpoints of this study are as follows:

Objectives	Associated Endpoints

 To evaluate the safety and tolerability of tapinarof cream, 1% in adults with plaque psoriasis 	
 Incidence, frequency, and nature of AEs and SAEs Change over time in clinical laboratory tests and frequency of clinically significant abnormal test results Change over time in vital signs and frequency of clinically significant abnormal results [REDACTED]

 To describe the efficacy of tapinarof cream, 1% over an extended period of time in adults with plaque psoriasis 	
 Proportion of subjects who experience a PGA ≥ 2 at least 1 time in the study and the median time from baseline to first worsening (PGA ≥ 2) for subjects entering the study with a PGA score of clear (0) Proportion of subjects who achieve a PGA score of 0 at least 1 time in the study [REDACTED] Duration of each treatment episode, defined as time from each treatment initiation/re-initiation to each subsequent treatment success (PGA score of 0). [REDACTED] Proportion of subjects who never achieve a PGA ≥ 2 throughout the study Proportion of subjects who never achieve a PGA score of 0 or 1 throughout the study [REDACTED] [REDACTED] Change and percent change from baseline in %BSA affected by visit (OC and LOCF) Change and percent change in PASI score by visit (OC and LOCF) [REDACTED]

 To describe the effect of tapinarof cream, 1% on psoriasis symptom severity and the associated impact on daily activities and attitudes in adults with plaque psoriasis 	
 Change in disease impact on daily activities, as measured by the Dermatology Life Quality Index (DLQI) total and individual dimension scores

3. STUDY DESIGN

3.1. Overall Design

This is a long-term, open-label, multicenter, study to evaluate the safety and efficacy of topical tapinarof cream, 1% in adults with plaque psoriasis. Subjects in this study completed treatment with tapinarof or vehicle in 1 of 2 pivotal Phase 3 pivotal efficacy and safety studies (Study DMVT-505-3001 or Study DMVT-505-3002). The study will consist of up to 40 weeks of treatment and a 4-week safety follow-up period.

At the completion of the Week-12 Visit of the pivotal study (Baseline [Day 1] in this study), eligibility of the subjects opting to enroll in this extension study will be confirmed. Study visits during the treatment period for all subjects will occur every 4 weeks (± 3 days). A Phone Call will be performed at Week 2 (Day 15). Unscheduled visits may occur, as needed. Subjects who withdraw from the study before Week 40 will return to the study center for an Early Termination Visit. The total duration of study participation will be approximately 44 weeks.

Subjects in the study will be treated as follows based on their PGA score from the Week 12 visit in the pivotal study (DMVT-505-3001 or DMVT-505-3002).

- Subjects entering with a PGA ≥ 1 will receive treatment with tapinarof cream, 1% until they achieve a PGA score of 0, at which time treatment will be discontinued and subjects monitored for durability of response. If/when disease worsening occurs, as evidenced by a PGA ≥ 2 , treatment will then be re-initiated and continued until a PGA of 0 is observed.
- Subjects entering with a PGA of 0 will have treatment discontinued and be monitored for durability of response. If/when disease worsening occurs, as evidenced by a PGA ≥ 2 , treatment will then be re-initiated and continued until a PGA of 0 is observed.
- This treatment and re-treatment pattern of use will be continued until the end of the study (ie, subjects may receive study treatment up until the Week 40 visit) (see Section 5.1.5.2).

Study drug will be dispensed, and subjects will be instructed on how to apply study drug. Subjects will apply the daily dose of study drug while at the site, under the supervision of site personnel, after efficacy and safety assessments have been completed.

Study drug will be dispensed to subjects during the study visits and will be administered at home between study visits as instructed by site personnel. Subjects will be instructed to apply study drug once daily to all affected areas, including newly appearing lesions and lesions or affected areas that improve during the study. Subjects will apply sufficient study drug to cover completely each lesion with a thin layer of study drug and will record the time of study drug application in a daily diary provided by the study site. (Note that subjects are allowed, but not required, to treat fingernails, toenails, palms, soles, and scalp lesions with study drug; however, efficacy analyses will not include assessment of improvement of psoriasis in these areas.) Subjects will be instructed to maintain the approximate dosing time chosen at the beginning of the study for their full study participation. Study drug application instructions will be reviewed at subsequent study visits. During subsequent study visits, subjects will apply the daily dose of study drug while at the study under the supervision of site personnel, after efficacy and safety

assessments have been completed. The time of the dose application and assessments will depend on the time of the study visit (either morning or afternoon visit). Therefore, the timing of the study visit may lead to a change in the subject's chosen dosing time; if this occurs, it will NOT be considered a protocol deviation; the subject should resume their chosen dosing time the day following any such clinic visit application.

Rescue medications may be initiated with consultation of the medical monitor.

Safety assessments will include AEs, local (application site) tolerability, clinical laboratory tests, vital signs, physical examinations, and investigator-assessed LTS. Efficacy assessments will include a 5-point static PGA (0-4 scale), %BSA affected, the PASI, and subject-reported DLQI.

Refer to Section 6 for descriptions of study procedures and assessments and Section 7 and the Schedule of Assessments (

[Table 1](#)) for timing of procedures and assessments.

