4.6.1. Reasons for Withdrawal from Study

Study drug will be discontinued for any of the following reasons:

- Subject has an AE that is considered to be related to study drug or procedures AND is severe enough to warrant treatment discontinuation, as determined by the Investigator (Section 8.1)
- Subject requires concurrent prohibited concomitant medication during the study. If, in the opinion of the Investigator and the study Medical Monitor, such medication will not interfere with the conduct or interpretation of the study or compromise the safety of the subject, then the subject may continue to receive study drug. If the subject is discontinued from study drug, they may remain in the study for safety assessments as needed, at the discretion of the Investigator and Medical Monitor.
- Pregnancy
- Any Grade 3 or 4 AE considered causally related to study drug (Section 8.2.2)

Study drug may be discontinued for any of the following reasons:

- Subject noncompliance
- Investigator noncompliance
- Discontinuation of the study at the request of the Sponsor, regulatory agency, or an Institutional Review Board (IRB)/Independent Ethics Committee (IEC)

If a subject meets a withdrawal criterion during treatment, an Early Termination Visit will be required (Section 7.7).

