5.6.2. Prohibited Medications and Nondrug Therapies

Medications and nondrug therapies that are prohibited throughout the study duration are as follows:

- **Biologic agents:** rituximab, ustekinumab, secukinumab, golimumab, ixekizumab, infliximab, adalimumab, alefacept, etanercept (list is not exclusive, contact Medical Monitor for questions)
- **Systemic treatments:** cyclosporin, interferon, methotrexate, apremilast, tofacitinib, mycophenolate, thioguanine, hydroxyurea, sirolimus, azathioprine, other systemic immunosuppressive or immunomodulating agents, fumaric acid derivatives, vitamin D3 and analogs (>5000 IU / day), retinoids (e.g., acitretin, isotretinoin), psoralens, corticosteroids, or adrenocorticotropic hormone analogs
- **Ultraviolet light:** therapy or prolonged exposure to natural or artificial sources of UV radiation (e.g., phototherapy, tanning beds/booths, or therapeutic sunbathing)
- **Topical treatments:** corticosteroids, antihistamines, immunomodulators, anthralin (dithranol), Vitamin D derivatives (e.g., calcipotriene, calcipotriol), retinoids (e.g., tazarotene), or coal tar
- **Drugs known to possibly worsen psoriasis (unless on a stable dose for >12 weeks):** beta blockers (e.g., propranolol), lithium, iodides, angiotensin-converting enzyme inhibitors, and indomethacin
- **Immunizations:** live, attenuated vaccines (inactivated or subunit vaccines are acceptable when required)
- **Other:** any Investigational products or procedures

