11.5 Prior and Concomitant Medications

Prior (within 30 days before Visit 1 and with stop dates prior to Visit 1) medications would have been captured in the pivotal studies and will not be presented in this study.

Concomitant (ongoing or with stop dates on or after Visit 1) medications will be listed by subject. If the medication is ongoing or the stop year is missing, the medication will be considered as received for the entire duration of the study. Concomitant medications that are ongoing as of the end of the pivotal studies will be displayed in a separate listing.

Medications will be coded using WHO-DD terminology. Concomitant medications will be summarized by WHO-DD Anatomical-Therapeutic-Chemical (ATC) classification and preferred term (PT), overall and by DB treatment group.

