11.7 Efficacy Endpoints

Efficacy endpoints are as follows:

For subjects entering the study with a PGA score of clear (0):

- Proportion of subjects who experience PGA ≥ 2 at least 1 time during the study.
- Proportion of subjects who never experience PGA ≥ 2 throughout the study.
- Time to first worsening (PGA ≥ 2), defined as days from date of Visit 1 date to the date of first occurrence of PGA ≥ 2 . Subjects who never experience PGA ≥ 2 throughout the study will be censored at the date of their last PGA assessment.

For subjects entering the study with a PGA score ≥ 1 :

- Proportions of subjects who achieve PGA = 0 at least 1 time during the study

• [REDACTED]

• [REDACTED]

[REDACTED]

For subjects entering the study with a PGA score ≥ 2 :

- Proportions of subjects who achieved PGA = 0 or 1 at least 1 time during the study.
- Proportions of subjects who never achieve PGA = 0 or 1 throughout the study.

The following endpoints will be summarized over subjects in ITT population:

- Duration (days) of treatment episodes, defined as time (days) from the date of each PGA ≥ 2 (or PGA ≥ 1 for the first episode) to 1 day before each subsequent treatment success (PGA = 0). The date of the last PGA assessment will be used as the end date for episodes ongoing at the end of the study.

- [REDACTED]
- [REDACTED] \geq [REDACTED]
- [REDACTED]
- [REDACTED]
- [REDACTED]
- [REDACTED] change and percent change from baseline in %BSA affected by visit (OC and LOCF).
- [REDACTED] change and percent change from baseline in PASI score by visit (OC and LOCF)
- [REDACTED] \geq [REDACTED]
- [REDACTED] \geq [REDACTED]
- [REDACTED] \geq [REDACTED]

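### Rescue and other prohibited psoriasis therapy is possible during the study, but no readable SAP endpoint rule reacts to it, so clearance reached on another drug can be counted as tapinarof efficacy

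*Protocol*

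**What the plan says.** Protocol 3.1, like the synopsis, states: "Rescue medications may be initiated with consultation of the medical monitor". No agent, trigger or consequence for the endpoints follows.

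Protocol 5.6.2 opens its list with "Medications and nondrug therapies that are prohibited throughout the study duration are as follows". The list covers biologics, systemic agents, ultraviolet light and topical treatments such as corticosteroids and vitamin D derivatives. It makes no exception for rescue.

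Protocol 4.6.1 makes stopping study drug the default when a subject needs a prohibited medication. There are two exceptions. If the investigator and the medical monitor judge that the medication affects neither the conduct or reading of the study nor the subject's safety, "then the subject may continue to receive study drug". Otherwise: "If the subject is discontinued from study drug, they may remain in the study for safety assessments as needed".

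In the SAP the readable endpoints depend on the measured value alone. For subjects entering with PGA ≥ 1, SAP 11.7 lists "Proportions of subjects who achieve PGA = 0 at least 1 time during the study". A treatment episode runs until the day before the next PGA of 0, or to the last PGA if still open. For subjects entering with PGA 0, those who never reach PGA ≥ 2 "throughout the study will be censored at the date of their last PGA assessment". SAP 7 defines only an ITT set, and SAP 8 gives only OC and LOCF. Other therapy appears only in the concomitant-medication outputs (11.5) and, where it is a deviation, in the deviation outputs (11.2). The word rescue does not appear in the SAP, and SAP 12 lists no change on the point.

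**The concern.** The study has no control arm, so the effect of another drug has nothing to cancel against. Subjects who need rescue are likely to be those doing poorly on tapinarof. If the other therapy works, it adds PGA 0 and PGA 0/1 results, lowers %BSA and PASI, and turns open treatment episodes into completed ones. Each of these shifts favours tapinarof, except that a rescued subject who clears late adds a long episode where there would otherwise have been a censored one.

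The sponsor's own text treats such therapy as confounding. Use of a prohibited psoriasis product in the pivotal study is an exclusion criterion (Protocol 4.3), and 4.6.1 asks whether a medication affects interpretation. Protocol 10 says the study is meant to show a favourable efficacy profile, and Protocol 10.5 and SAP 9 plan an interim data-cut for the marketing application. The efficacy tables will therefore be read as the effect of tapinarof.

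**Working it through.** The plan gives no figure to reproduce, because it states no rescue rate and does no testing. The check has four steps.

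**1. Is any rule triggered by other therapy?** The SAP sections that could contain one were read for it.

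- Analysis set (SAP 7): all enrolled subjects; nothing on other therapy.
- Missing data (SAP 8): OC and LOCF; nothing on values after other therapy.
- Endpoints (SAP 11.7, readable part): defined by PGA, %BSA or PASI value; time to first worsening is censored only at the last PGA.
- Analyses (SAP 11.8): Kaplan-Meier and descriptive summaries; no condition on other therapy.
- Medications and deviations (SAP 11.5, 11.2): listed and summarised, not linked to endpoints.

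So under the readable rules a PGA of 0 reached on another drug counts as clearance and closes an episode.

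**2. How far can one such value travel?** About 300 of an estimated 850 subjects are expected to complete: 300/850 = 35.3%, leaving 850 − 300 = 550 (64.7%) whose Week 40 LOCF value would come from an earlier visit. The Early Termination visit includes PGA, %BSA and PASI (Protocol 7.7), and SAP 10.5 renumbers it as the next scheduled visit. An early-termination value recorded after other therapy began can therefore become that subject's Week 40 result for PGA, %BSA and PASI, all of which SAP 11.8 summarises by LOCF.

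**3. Size for ever reaching PGA 0.** Let r be the share of subjects entering with PGA ≥ 1 who take such therapy and would not otherwise have cleared. Let c be their chance of reaching PGA 0 on it. Inflation = r × c. Both are assumptions.

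| r | c = 20% | c = 40% | c = 60% |
|---|---|---|---|
| 2% | 0.4 points | 0.8 points | 1.2 points |
| 5% | 1.0 points | 2.0 points | 3.0 points |
| 10% | 2.0 points | 4.0 points | 6.0 points |

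The ends of the range are 0.02 × 0.20 = 0.004 and 0.10 × 0.60 = 0.06. The documents do not say how many subjects enter with PGA ≥ 1, so this cannot be turned into a number of subjects.

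**4. Size for time to first worsening.** This endpoint covers only subjects entering with PGA 0. Assume a true median of 16 weeks, so the weekly hazard is h = ln 2 / 16 = 0.0433. A share r of these subjects takes other therapy from entry, which multiplies the hazard by k. Then S(t) = (1 − r)·exp(−ht) + r·exp(−hkt). If the therapy prevents worsening (k = 0), the apparent median is ln[(1 − r)/(0.5 − r)]/h. At r = 10% this is ln(0.9/0.4)/0.0433 = 18.7 weeks.

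| r | Apparent median, k = 0.5 to k = 0 | Not worsened by Week 40 (true 17.7%) |
|---|---|---|
| 2% | 16.19 to 16.48 weeks | 18.2% to 19.3% |
| 5% | 16.49 to 17.25 weeks | 18.9% to 21.8% |
| 10% | 17.01 to 18.72 weeks | 20.1% to 25.9% |

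For true medians of 12 to 24 weeks the median lengthens by 0.14 to 0.71 weeks at r = 2% and by 0.75 to 4.08 weeks at r = 10%. Therapy from entry is an extreme assumption, so later starts would give less.

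**The case against.** The strongest reply is that Protocol 4.6.1 already keeps most interfering therapy out. Stopping study drug is the default, continuation needs a judgement of no interference, and remaining in the study is for safety assessments. This stands, and it makes the prohibited-medication route narrow. It does not cover the rescue sentence, which carries no such limit.

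A second reply is that the study is descriptive, is sized on safety exposure, and will list and summarise concomitant medications and deviations, so use of other therapy would be visible. Analysing outcomes regardless of rescue is also a recognised strategy. This lowers the severity. But the SAP does not state that it has chosen that strategy. In a single-arm study it answers a different question: outcome on tapinarof plus whatever else was given.

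Several stronger readings are tempting and are not supported:

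- **That clearance on other drugs will be reported as tapinarof efficacy.** The documents support only that it can be. Parts of SAP 11.7 are redacted, and the revision history says the duration of treatment success was redefined. A rule there cannot be excluded.
- **That off-drug durability is broadly distorted.** The readable event is the first PGA ≥ 2, and the protocol's response to it is re-treatment with tapinarof. Therapy given after that visit cannot change the endpoint. The bias needs other therapy started while a subject who entered clear is still at PGA 0 or 1.
- **That the SAP cannot separate values before and after rescue.** SAP 11.5 does say of some drugs that "the medication will be considered as received for the entire duration of the study". That rule applies to medications that are ongoing or lack a stop year, and it sits in the concomitant-medication outputs. Start dates are required source data under Protocol 11.1.5.
- **That skin reactions will be treated with topical corticosteroids on plaques.** Protocol 1.3.1.1 says only that "study treatment will be interrupted and an appropriate treatment provided". The agent is not named, and 5.6.2 prohibits topical corticosteroids.
- **That the inflation could reach 9 points.** A reader might take 15% of all 850 and a 60% clearance rate (0.15 × 0.60). The endpoint excludes subjects entering with PGA 0, some rescued subjects would have cleared anyway, and nothing in the documents supports those rates.

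**Conclusion.** The concern holds in limited form. The protocol allows undefined rescue in one place and bars the likely agents in another, and no readable SAP rule says what happens to efficacy data afterwards. The main exposure is in the clearance endpoints, episode duration, and the OC and LOCF summaries of PGA, %BSA and PASI. Time to first worsening is a lesser exposure.

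The size is unknown. The 0.4 to 6 points for ever reaching PGA 0 rests wholly on assumed r of 2–10% and c of 20–60%, and at r of 2% or less the effect is small. The durability figures also rest on an assumed exponential model. Severity is moderate: the estimates are descriptive, but the likely direction favours tapinarof and the gap is cheap to close.

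**What to change.** **Protocol.** Sections 3.1 (and the synopsis), 4.6.1 and 5.6.2 must be reconciled so that they state one position on rescue. Which position is for the sponsor to decide.

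**SAP 11.7 and 11.8.** Define a flag from the recorded start date of psoriasis-active rescue or prohibited therapy, using the actual date and not the 11.5 whole-study convention. Then:

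- (a) Do not count a later PGA 0 or 0/1 as success, and do not let it close a treatment episode. State how the subject is then handled in the Kaplan-Meier estimate, for example event-free to the last PGA. Limit this to the efficacy analysis, because SAP 11.4 builds expected exposure days and compliance on the same episodes.
- (b) Exclude later PGA, %BSA and PASI values from OC, and in LOCF carry forward the last value before that therapy. SAP 8 bars carrying baseline forward, so a subject with no earlier post-baseline value has no LOCF result; say so.
- (c) For time to first worsening, keep the PGA ≥ 2 event. Add a sensitivity analysis in which starting such therapy also counts as an event. Making that the main analysis would redefine the protocol's event.
- (d) Report the number of subjects affected, and keep the as-observed tables as supportive.

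The cost is one derived flag from records already collected, some SAP wording before database lock, a clarifying protocol edit, and probably slightly less favourable figures.
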